## The Social Skills Improvement System (SSIS)81

The SSIS (Gresham, 2008) is a parent and self-report measure that assesses social skills (i.e., communication, responsibility, self-control, cooperation), competing problem behaviors (e.g., externalizing, internalizing, bullying), and academic competence (e.g., motivation to learn). Raw scores and standard scores will be utilized to explore the relationship between social skills and participation in the intervention. It will be completed by parents and adolescents at the baseline, post-treatment, and 6-month follow-up assessment visits.

**Friendship Qualities Scale (FQS)**. The Friendship Qualities Scale is a teen self-report measure that assesses the quality of best friendships. It uses a Likert scale on each of the 23 items, from 1 to 5. Teens are instructed to identify their best friend and keep this friendship in mind when completing this measure. It has 5 subscales: companionship, closeness, help, security, and conflict.

**Test of Adolescent Social Skills Knowledge (TASSK)**. The Test of Adolescent Social Skills Knowledge is a 26-item criterion-referenced test developed for PEERS to assess the teen's knowledge about the specific social skills taught during the intervention. Teens are presented with sentence stems and asked to choose the best option from two possible answers.

Quality of Socialization Questionnaire (QSQA and QSQP). The Quality of Socialization Questionnaire consists of 12 items, both teen and parent versions, to assess the frequency of get-togethers with peers over the previous month. It also assesses the level of conflict during these get togethers.

**The Community Integration Scale** is a 33-item measure that documents a person's involvement in their community. There is a parent version for their child, and a self-report version.

**Child Concentration Inventory, Second Edition (CCI-2)**. The CCI-2  is a child-report measure of SCT symptoms. The CCI-2 consists of 16 items that are rated on a four-point scale (0 = never, 1 = sometimes, 2 = often, 3 = always). There is evidence supporting the reliability and validity of the CCI-2 in children and adolescence .

**Child and Adolescent Behavior Inventory (CABI)**. The CABI SCT module was derived from a meta-analysis which examined the stability and reliability of SCT items derived from various measures. Parents will complete the CABI  SCT module. Recent studies support the reliability and validity of the CABI .

**Outcomes Survey.** This survey, completed by parents via Redcap survey, assesses their child's current status in education, work, independent living, social connectedness, and daily living skills.

### **DURATION:**

Recruitment will begin in month 10 of Year 1. We will recruit 4 cohorts of 14 adolescents with ASD and their parents that will then be randomized to Surviving and Thriving in the Real World (STRW) or Program for the Evaluation and Enrichment of Relational Skills (PEERS). We plan on recruiting a total of 56 adolescent and parent participants during Years 1-4. All participants will complete an eligibility assessment, baseline assessment, 14-week intervention (STRW or PEERS), post-treatment assessment, and a 6-month follow-up assessment. The 3 DPDS (two weekdays and one weekend day) will be completed by both adolescent and parent participants within a week of the baseline, post-treatment, and 6-month follow-up assessment visits.

### **DATA ANALYSIS/METHODS:**

### **Data Entry Procedures**

Physical data, including test protocols that are collected at CCHMC will be housed in locked file cabinets in the PI's lab space. This space will be locked at all times. Only the principal investigator or other IRB approved members of the CCHMC research team will have access to the physical data.

All data for each participant will be labeled with a unique ID number. Source documents and protocols may be scanned to a PDF and stored as an electronic file in the secured CCHMC server. Data will be entered into REDCap, a secure, web-based application designed to support data capture for research studies, providing: 1) an intuitive interface for validated data entry; 2) audit trails for tracking data manipulation and export procedures; 3) automated export procedures for seamless data downloads to common statistical packages; and 4) procedures for importing data from external sources.

After a family has completed participation, the physical files will be stored in locked cabinets at CCHMC. Audio and video recordings will be uploaded to a secure CCHMC server or external hard drive which only IRB approved staff will have access to. The hard drive will remain locked in a cabinet in staff office. Data in the electronic database are available indefinitely to qualified researchers who have access to the database. Thus, unless a participant indicates that they no longer consent to making their data available for analysis, deidentified electronic data will remain available for research in the database indefinitely. Audio recordings of parent interviews, video recordings of assessments, and video recordings of group sessions will be destroyed after data analysis has been completed and the study is closed. Physical data obtained from participants will also be housed by the PI indefinitely given that data collection has concluded. There may be reason to move the hard copy files to a different storage location at some point (e.g., P.I. change/move) either during or after the study. This will be approved through the IRB and all protected health information will remain secure. If at any time during or after the conclusion of the study, a participant requests that their data not be used, the PI will immediately destroy all physical data and also ensure that all electronic data connected to that participant be removed from the database.

### **Analyses**

**Power Analyses:** The feasibility RCT is being conducted with the intent of examining the differences in DLS to be expected. Few studies have examined the trajectory of DLS in individuals with ASD, and no studies have examined how DLS develop during adolescence. Power calculations focused on the anticipated increase or improvement in the age equivalence scores of each of the Vineland-3 DLS subdomains for the STRW group and control group. We used conservative estimates of change in DLS subdomain age equivalence scores for our sample size estimation, even though a recent pre-post trial and pilot RCT on STRW found a mean improvement of 2.3 to 2.6 years across the 3 subdomains from baseline to post-treatment.

**Aim 1:** For each Vineland-3 DLS subdomain, we anticipate that adolescents in the STRW group will have a mean improvement of 11 months (a mean gain in age equivalence of 11 months) at post-treatment compared to a mean improvement of 4 months in the control group. Assuming a conservative pooled standard deviation of 8.4, we will have 80% power to detect the above effect size (of 0.8) with 24 participants per group. Accounting for a potential 15% drop out rate, the effective sample size is 28 per group. Based on our past studies, we would expect the mean improvement in the STRW group to be 16 months, but we wanted to be conservative and estimate the sample size based on detecting a mean improvement as small as 11 months in the STRW group.

**Aim 2**: For each DLS subdomain, we anticipate that all participants who receive the STRW treatment will maintain treatment gains from post-treatment to 6-month follow-up.

A secure REDCap database has been built and will be maintained for all measures administered in the current study. The primary DLS outcome measure for Aims 1 and 2 at post-treatment and 6-month follow-up is change in Vineland-3 DLS domain and subdomain raw scores and age equivalent scores. The secondary DLS outcome measure is change in score on the goals targeted on the DLS-GAS. The expectation is that the STRW group will have an increased change in score on both the Vineland-3 and DLS-GAS as compared to the control group (PEERS). The exploratory DLS outcome measures are (1) Daily phone diaries that assess the daily behaviors/experiences of adolescents with ASD (e.g., number of DLS completed for adolescents with ASD over a 24-hour period); (2) number of incorrect and correct steps for the task analysis of specific DLS as assessed by the direct behavioral observation measure; and (3) parent report and self-report of DLS as assessed by the ABAS-3. All analyses will be done using SPSS Version 20.0. Univariate statistics such as means, medians, and standard deviations will be computed for each variable to allow for examination of any outliers, variables that are not normally distributed, and heterogeneous variance between groups. The comparability of the STRW group and control group (PEERS) prior to treatment will be assessed using chisquare tests for categorical variables and t-tests for continuous variables.

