### **PURPOSE OF STUDY:**

The current study seeks to develop the first DLS intervention package for high functioning adolescents with ASD and evaluate its effectiveness. We hope to further refine the STRW intervention by conducting an ORBIT (Obesity-Related Behavioral Intervention Trial) Phase 2b feasibility RCT (Randomized Clinical Trial). This RCT will test the preliminary effectiveness of STRW in 56 adolescents (14-21 years) with high functioning ASD as compared to a robust evidence-based social skills intervention (Program for the Evaluation and Enrichment of Relational Skills - PEERS). The current proposal represents a critical step toward improving the adult outcome of individuals with ASD.

Aim 1: Examine the preliminary effectiveness of STRW in a feasibility RCT. Participants randomized to STRW will demonstrate improvement on targeted DLS on the Vineland-3, pre- to post-treatment as compared to PEERS (control). The secondary outcome measure will be goal attainment scaling. Exploratory outcome measures (i.e., daily phone diaries, direct behavioral observations, and self-report of DLS) will be examined. Aim 2: Assess maintenance of treatment gains at 6-month follow-up. Participants in STRW will maintain greater DLS as compared to PEERS (control).

Aim 3 (Exploratory): Explore how social skills, executive functioning, psychopathology, and parenting factors, which have been linked to DLS, are affected by participation in STRW.

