
#### PROCEDURES:

Procedures will consist of running 4 cohorts of 14 high functioning adolescents with ASD (IQ≥70) and their parents in the STRW group or a social skills group (i.e., Program for the Evaluation and Enrichment of Relational Skills –PEERS ). Approximately 7 adolescents with ASD and their parents will participate in each STRW and PEERS group. Thus, across 4 cohorts, the goal will be to enroll 28 adolescents in both the STRW and PEERS groups during Years 1-4.

The parent will complete the Vineland-3 and the adolescent will be administered the SB-5 and the ADOS-2 if they do not have one that has been completed at CCHMC within the past 2 years. If the eligibility assessment indicates that inclusion criteria has been met, the adolescent and parent participants will complete the baseline assessment. At the baseline assessment, parents will complete an in-depth clinical interview to assess the DLS that will be targeted in the intervention and a questionnaire packet. Adolescent participants will complete activities to directly assess their DLS and a questionnaire packet. All procedures for the baseline visit except for the ADOS, IQ test, and Behavioral Observation may be conducted via telehealth. Adolescent and parent participants will also complete 3 DPDs (two weekdays and one weekend) after completing the baseline assessment visit. Once an eligible cohort of 14 adolescents with ASD has been obtained and completed measures at the baseline assessment visit, adolescents will be randomly assigned to either the STRW or PEERS intervention using a stratified randomized block design with IQ (≥85 and <85) and age (≥17 and <17) as strata variables to ensure balanced group assignment for each cohort. Thus, across 4 cohorts, the goal will be to enroll up to 28 adolescents in both the STRW and PEERS groups during Years 1-4.

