### **MEASURES:**

### Baseline only:

**The Background History Form** will collect demographics including race, ethnicity, maternal education, household income, and current treatments and services. Information obtained from the Background History form will be utilized to describe the sample and as covariates in statistical analyses.

The Autism Diagnostic Observation Schedule, 2nd Edition (ADOS-2) is a well-established clinician-administered diagnostic assessment. Either Module 3 or Module 4 of the ADOS-2 will be administered to all

adolescents at the baseline assessment to confirm ASD diagnosis. A previous ADOS may be used to confirm eligibility if was done less than 2 years ago or up to the discretion of the P.I. [name] is research reliable and a certified trainer of the ADOS-2. In addition to being suited to screen for eligibility, the ADOS-2 will be used to describe the sample and as a predictor in statistical analyses.

**The Stanford Binet Intelligence Scales, 5th Edition** (SB5) will be used to assess verbal, nonverbal, and overall cognitive abilities and will be administered at the baseline assessment. The SB5 will be used to confirm that the adolescent participant meets the inclusion criteria of a full-scale IQ >70 and will also be used as a predictor in statistical analyses.

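### No between-arm model is named for the primary Vineland-3 change; adjust for the baseline score and randomisation strata, and account for treatment groups

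*Combined protocol and SAP*

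**What the plan says.** - **Outcome.** Under DATA ANALYSIS/METHODS, Analyses: "The primary DLS outcome measure for Aims 1 and 2 at post-treatment and 6-month follow-up is change in Vineland-3 DLS domain and subdomain" raw and age-equivalent scores. The same paragraph expects more change in STRW than in PEERS. The only tests it names, chi-square and t-tests, are for comparability of the arms before treatment.
- **Hypotheses.** PURPOSE OF STUDY makes a between-arm claim for Aim 1 at post-treatment and for Aim 2 at 6 months: "Participants in STRW will maintain greater DLS as compared to PEERS (control".
- **Sizing.** The power paragraph for Aim 1 compares mean improvements of 11 and 4 months: "Assuming a conservative pooled standard deviation of 8.4", 80% power with 24 per group. It continues: "Accounting for a potential 15% drop out rate, the effective sample size is 28 per group". It treats 11 months as a cautious figure: "we would expect the mean improvement in the STRW group to be 16 months". No test, alpha or sidedness is given.
- **Covariates.** MEASURES, Baseline only: "Information obtained from the Background History form will be utilized to describe the sample and as covariates in statistical analyses". Of the SB5 it says that it "will also be used as a predictor in statistical analyses", and the ADOS-2 entry is similar. None of these statements is tied to a model or an outcome.
- **Design.** PROCEDURES stratifies randomisation by IQ (cut at 85) and age (cut at 17) within each of four cohorts. It adds: "Approximately 7 adolescents with ASD and their parents will participate in each STRW and PEERS group".

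**The concern.** The primary comparison is described only as a difference in change, and it is sized that way. The baseline score is collected on everyone and the strata are built into the randomisation, yet no analysis is said to use either. Adjusting for the baseline value of an outcome is, in large samples, never less precise than comparing raw change, and it is usually more precise. The plan therefore leaves a cheap gain unused. It also leaves the model and covariates open at both time points, against a long list of candidate covariates.

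Naming a model raises a second matter. Both arms are delivered in groups, so outcomes within a group may be correlated. A regression that ignores this gives standard errors that are too small if the correlation is above zero.

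**Working it through.** **Inputs from the plan.** Difference 11 − 4 = 7 months; SD 8.4, read as the SD of change in months because the plan gives no unit; 24 analysed per arm.

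**Assumptions.** Two-sided 0.05. The baseline-to-post correlation ρ is not in the documents, so 0.5, 0.7 and 0.9 are shown. The ICC is not in the documents either.

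**1. The plan's own figure.** The standard error of the difference in change is 8.4 × √(2/24) = 2.425. The noncentrality is 7/2.425 = 2.887 on 46 df, which gives 80.7% power. The stated 80% with 24 per group is reproduced. It rests on the unrounded effect size 7/8.4 = 0.833; at the printed 0.8, power is 77.4%. At the expected 16 v 4 months (12/2.425 = 4.949), power is 99.8%.

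**2. Baseline adjustment.** Let k be the post SD divided by the baseline SD. The variance of the adjusted comparison relative to raw change is f = k²(1−ρ²)/(k²+1−2ρk). At k = 1 this is (1+ρ)/2. Power uses noncentrality 2.887/√f on 45 df.

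| | ρ = 0.5 | ρ = 0.7 | ρ = 0.9 |
|---|---|---|---|
| f at k = 1 | 0.75 | 0.85 | 0.95 |
| Power, baseline adjusted, k = 1 | 90.3% | 86.5% | 82.6% |
| f at k = 1.25 | 0.893 | 0.981 | 0.950 |
| Power, baseline adjusted, k = 1.25 | 84.8% | 81.4% | 82.6% |

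The comparator is 80.7% throughout. At k = 1/ρ, f = 1 and the gain is zero.

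**3. Adding the two strata.** The model now has three covariates and 43 df. If the strata are non-prognostic and all three covariates differ between arms by chance, the variance is multiplied by 45/(45−3) = 1.071. At k = 1, power is then 88.3%, 84.1% and 79.9%. The fair comparator is baseline adjustment alone with chance imbalance in baseline (variance × 45/44): 89.7%, 85.8% and 81.7%. The strata therefore cost 1.4 to 1.8 points, and at ρ = 0.9 the model is about 0.8 points below unadjusted change. At k = 1.25 the three-covariate figures are 82.3%, 78.6% and 79.9%; at k = 1/ρ, 77.8%.

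**4. Treatment groups.** Four cohorts with one group per arm make 8 groups, with about 6 analysed in each (24/4). At ICC 0.05 the design effect is 1 + 5 × 0.05 = 1.25. A test that ignores it rejects with probability of about 2 × [1 − Φ(1.96/√1.25)] = 2 × [1 − Φ(1.753)] = 8.0%. At ICC 0.10 the design effect is 1.5 and the result is 11.0%. Simulating the three-covariate model with no group term (8 groups of 6, ρ = 0.7, 8,000 runs per ICC) gave 5.0%, 8.2% and 11.3% at ICC 0, 0.05 and 0.10. Adding cohort did not help (8.5% at ICC 0.05): each cohort contains one group per arm, so a cohort effect common to both arms cannot absorb differences between groups in the same arm.

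The power figures in steps 1 to 3 make no allowance for clustering. With the variance multiplied by 1.25 and the df unchanged, unadjusted power is 71.5% and baseline-adjusted power 83.1%, 78.2% and 73.6%.

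**The case against.** The strongest reply is that a named t-test on change would close the gap equally well and is what the sizing matches, so choosing covariate adjustment is preference. In part this stands: any model fixed in advance removes the freedom to choose later. What remains is that baseline adjustment is the better use of data already collected, except where the SD ratio is near 1/ρ.

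A second reply is that adding covariates at 48 analysed participants need not gain precision. That is correct. The gain belongs to the baseline score. The strata go in because randomisation used them, and step 3 shows cases where the model falls slightly below unadjusted change.

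A third is that this is a feasibility trial of preliminary effectiveness. That lowers the stakes, but the plan states between-arm hypotheses and powers Aim 1.

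Three stronger readings are tempting and not supported:

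- **The change comparison is biased.** In a randomised trial, an unadjusted comparison of change is not biased for want of baseline adjustment.
- **The trial falls short of its stated power.** The 80% reproduces, and the plan expects a larger effect than the one it sized on.
- **The open model means an inflated error rate.** Taking the smallest p-value from a t-test on change, a t-test on the post score and a baseline-adjusted model gives about 10% type I error in simulation (9.7% to 10.2% at ρ 0.5 to 0.8). That shows what the freedom could cost. Nothing in the documents says that the model will be chosen from the results.

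**Conclusion.** The point holds as an improvement in precision and prespecification that should be made. No between-arm model is named at post-treatment or 6 months, and nothing commits the comparison to the baseline score or the strata. Baseline adjustment raises power from 80.7% to between 82.6% and 90.3% over ρ 0.9 to 0.5, given two-sided 0.05, an SD of change of 8.4 months, equal variances and no clustering. The gain disappears as k approaches 1/ρ. Confidence in its size is moderate because ρ, k and the ICC are all assumed.

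The model is adequate only if it deals with treatment groups. The 8% error rate is conditional on an ICC of 0.05; with no within-group correlation the problem does not arise.

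**What to change.** For each Vineland-3 DLS score analysed, at post-treatment and at 6 months, prespecify:

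- A linear model of the score on arm, the baseline value of that score, IQ stratum (<85, ≥85) and age stratum (<17, ≥17), with participants analysed in the arm assigned. Modelling change with the same terms gives the same arm effect, so change can stay as the outcome label. A repeated-measures model with the same baseline adjustment is an acceptable equivalent.
- An allowance for treatment group, for example a random effect with small-sample degrees of freedom. At minimum, report a sensitivity analysis over a range of ICCs. Cohort may be added but does not replace this.
- A statement that the baseline comparability tests will not be used to choose covariates.

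**Cost.** Analysis-plan wording and somewhat more analysis work; the data are already collected. Chance imbalance in non-prognostic strata costs about 2 points of power. Allowing for groups also has a price: if the reference distribution had only 8 − 2 = 6 df (critical value 2.447) and the ICC were 0.05, the noncentrality 2.887/√(1.25f) at k = 1 gives 70.1%, 64.8% and 60.2% with baseline adjustment, against 58.0% without. That is a cautious bound on an assumed ICC, and the advantage of baseline adjustment remains.

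This change does not settle which of the listed scores is primary, multiplicity across them, or the handling of missing follow-up scores.

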## **FACILITIES and PERFORMANCE SITES:**

The Division of Behavioral Medicine and ClinicalPsychology (BMCP) at Cincinnati Children's Hospital Medical Center (CCHMC) will serve as the project site for the recruitment and assessment of participants for the study. Assessment rooms (approximately 225 sq. ft.) within DDBP will be used for the assessments. The video and audio recording equipment needed for the project will be housed in this space for the duration of the project.

The in-person STRW treatment group and PEERS group meetings will be held in the Schubert Research Clinic through the Clinical Translational Research Center (CTRC) in the T building on CCHMC's campus. We will be using the Metabolic kitchen for the cooking portion of the group, as well as 2 other conference rooms for the parent and adolescent weekly meetings.

### **DATA SAFETY MONITORING PLAN:**

The subject pool is a vulnerable population (i.e., adolescents with ASD) and there is the potential for adverse events. Therefore, we recognize the need for a careful data and safety monitoring plan to ensure the well-being of the adolescents in this study and scientific integrity of the project. The PI and her primary mentor will review and evaluate the accumulated data for participant safety, adverse events, study conduct and progress [as part of their weekly meetings. They will make recommendations to the appropriate regulatory agencies (i.e., IRBs, NIH) concerning continuation, modification, or termination of the study. In addition, provision will be made for an emergency meeting should any serious adverse events occur. The PI will prepare reports to be reviewed with her primary mentor and statistician at each quarterly meeting. Further, an independent safety

monitoring committee has been established to ensure the well-being of participants in the study and maintain the scientific integrity of the project. [name] is a developmental psychologist and [name] is a developmental pediatrician. These individuals are not associated with this research project and work independently of the Pl. They are not part of the key personnel involved in this grant. No member of the Committee has collaborated or co-published with the Pl within the past three years. They are qualified to review the patient safety data generated by this study because of their unique expertise in research with ([name]) and clinical care ([name]) of youth with ASD and other developmental disabilities. The Pl and Mentor will meet with the independent safety monitoring committee every six months and review all reports listed below throughout Years 1-4 when participants are being actively seen or followed.

The reports will include a summary of the following topics: Performance Monitoring: A report of subject recruitment, comparison with targeted recruitment, retention, protocol adherence, and quality of data collection procedures. Safety Monitoring: A review of safety of the subjects, including confidentiality, any adverse events or side effects related to the treatment or study participation. Treatment Monitoring: A report of treatment integrity and compliance, which will include attendance to assessment and treatment visits. This will also include the data from the personnel who will be reviewing videotapes for the behavioral intervention. Stopping Rules: If a serious adverse event as a result of participation in the study occurs, participant accrual will discontinue until the PI and her primary mentor have reviewed the information with the independent safety monitoring committee and the subject has received adequate care. Participant recruitment will commence again only after the PI has been given permission to continue. In addition, if the subjects in the treatment group are not showing beneficial response to treatment (i.e., no significant change in skills), the PI and her primary mentor will meet with the independent safety monitoring committee and may make the determination that the study be modified or discontinued. Finally, if during the course of the trial, new information becomes available about the effects of behavioral intervention or other major advances in the treatment of DLS for adolescents with ASD that significantly impacts treatment approaches, the PI and her primary mentor will review the evidence with the independent safety monitoring committee to make a decision about discontinuing the trial.

